ARGX-113-2211 is a long-term, single-arm, open-label, multicenter extension study of the pSS-qualifying efgartigimod studies designed to evaluate the long-term safety of efgartigimod in adult patients with pSS. Participants will be enrolled from both active and placebo arms of qualifying efgartigimod studies and receive efgartigimod 10 mg/kg over 48 weeks in the extension study without knowledge of their treatment assignment in the qualifying study. Eligible participants must have completed the treatment period of the qualifying study and must not have permanently discontinued the IMP in that study.

Brief Summary:

Participants will receive efgartigimod 10 mg/kg by IV infusion either Q2W or QW. The dosing regimen is based on whether the participant is a responder or nonresponder. Responder status will be determined by clinESSDAI assessments conducted on day 1, week 16, and week 24 and using the baseline of the qualifying study. Participants who are not responders at week 24 will be evaluated by PI for therapeutic failure. If a participant is a therapeutic failure, they will discontinue study treatment. If a participant is not a therapeutic failure, they will continue QW dosing regimen, and a clinESSDAI will be conducted at weeks 32, 36, 40, and 44 until confirming responder status and switching to Q2W dosing regimen. The PI will continue to evaluate the participant for therapeutic failure.

The study's primary objective is to assess the long-term safety of efgartigimod in participants with pSS. Additional assessments will be conducted, and blood samples collected to assess the effectiveness of efgartigimod at treating pSS, the PD effect of efgartigimod, and the immunogenicity of efgartigimod. Blood samples will also be collected to monitor the concentration of efgartigimod in blood over time.

Number of Participants:

Up to approximately 30 subjects who have completed the efgartigimod pSS study (ARGX-113-2106) will be enrolled for in the OLE study (ARGX-113-2211).

Note: *Enrolled* means the participant agrees to participate in the clinical study by completing the informed consent process.

[figure not shown]
Study Arms and Duration:

Each participant will participate in the following study periods:

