2. INTRODUCTION

Participants will be enrolled from both active and placebo arms of qualifying efgartigimod studies in adult patients with pSS. The protocol will be amended to add additional studies at a later date.

In qualifying study ARGX-113-2106, the efficacy and safety of efgartigimod in adult patients with pSS was evaluated using a randomized, double-blinded, placebo-controlled study design. Participants were randomized to receive efgartigimod IV 10 mg/kg or matching placebo in a 2:1 ratio. The IMP (efgartigimod or matching placebo) was administered during the treatment period in approximately 1-hour IV infusion QW by site or a home nurse. The final dose was administered at week 23. At week 24, eligible participants from ARGX-113-2106 may roll over into the present single-arm OLE study: ARGX-113-2211.

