4.3. Justification for Dose

Doses of efgartigimod 10 mg/kg either QW or Q2W will be administered. For responders a Q2W regimen has been selected to evaluate whether a less frequent dosing regimen can maintain clinical efficacy, while the QW regimen for nonresponders targets efgartigimod's to achieve a near maximal total IgG reduction (PD effect), thereby maximizing the chance of a clinical response on the efficacy outcomes in nonresponders.

As the hypothesis for treating pSS with efgartigimod is to reduce the pathogenic autoreactive IgG, the selected doses and dose regimen target a nearly maximal PD effect (ie, reduction of pathogenic IgGs). The chronic nature of pSS reflects the need for chronic treatment to maintain pathogenic IgG autoantibody suppression and symptom reduction.

The cumulative data from a phase 1 study in healthy adult subjects; phase 2 studies in participants with gMG, ITP, and pemphigus; phase 3 studies in gMG; and PK/PD modeling results demonstrate that a 10 mg/kg efgartigimod dose administered QW through IV infusion achieved 60% to 70% total IgG reduction, including the reduction of pathogenic autoantibodies. Maximal IgG reduction was associated with clinical efficacy observed in gMG, ITP, and pemphigus studies. Furthermore, this dose has been safe and well-tolerated in all study populations and has demonstrated similar PK and PD profiles across indications. Accordingly, the 10 mg/kg IV dose regimen (QW or Q2W) was selected for this study.

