6.2. Baseline

Unless otherwise specified, baseline is defined as the last available non-missing measurement from the parent study 2106. Refer to [appendix 1](#) baseline for details. These baseline observations could be either from week 24 or prior visits of ARGX-113-2106. All baseline assessments will be performed before first administration of efgartigimod in ARGX-113-2211, if applicable. The baseline of ECG parameters should come from the same date. If an individual

confidential and proprietary to IQVIA Holdings Inc. and its subsidiaries. Unauthorized use, disclosure or reproduction is strictly prohibited.

ECG parameter is not reported on the latest date prior to 1st IMP infusion within the extension study, leave blank. Assessments do not need to be repeated if they are performed as part of the last visit of the qualifying study. Assessments performed on the same day as the first IMP administration but without time information collected or with time information exactly equal to the time of first IMP administration and which are planned predose will be considered as predose. For parameters related to questionnaires, the baseline is the last value before or at the day of first administration of the IMP, independent of the time of administration. In case the participant never received IMP, the date/time of enrolled will be used instead of first IMP administration date/time. Adverse Events (AEs) and medications commencing on the reference start date will be considered post-baseline unless otherwise indicated based on available start date/time combination or collected electronic case report form (eCRF) information that identifies the individual event/medication as starting prior to first IMP administration.

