The proportion of participants with improvement of ≥ 3 points in score and the proportion of participants having ESSDAI score of < 5 at week 24 will be provided, along with exact 90% CIs and for each of these two endpoints.

Copyright © 2009, 2010, 2012, 2016, 2018, 2019, 2021, 2024 IQVIA. All rights reserved. The contents of this document are confidential and proprietary to IQVIA Holdings Inc. and its subsidiaries. Unauthorized use, disclosure or reproduction is strictly prohibited.

13.1.3. Proportion of Participants with Minimal Clinically Important Improvement in clinESSDAI: Improvement of ≥ 3 Points in clinESSDAI Score at Week 24 and 48 & Proportion of Participants with Low Disease Activity: clinESSDAI score of < 5 at Week 24 and 48

As explained in Section 14.2.1.1 of SAP, the ClinESSDAI includes all ESSDAI domains except the biological domain.

The proportion of participants with improvement of ≥ 3 points in clinESSDAI score and the proportion of participants having clinESSDAI score of < 5 at week 24 and 48 will be provided, along with exact 90% CIs and for each of these two endpoints.

13.1.4. Proportion of Participants with Minimal Clinically Important Improvement in ESSPRI: Decrease of 1 Point or $\geq 15\%$ at Week 24 and 48

The Information on the derivation of ESSPRI total score is provided in Section 14.2.1.1.

The proportion of participants with decrease of 1 point or $\geq 15\%$ in ESSPRI total score at week 24 and 48 will be provided and along with exact 90% CIs for each of these two endpoints.

13.1.5. Change in ESSDAI Score, clinESSDAI Score and ESSPRI Score at Week 24 and 48

These scores will be descriptively summarized for actual scores and changes from baseline in ESSDAI, clinESSDAI, and ESSPRI at scheduled timepoint of week 16, 24, 36 and 48. In addition, the same analysis in clinESSDAI and ESSDAI will be assessed for three subgroups (mutually exclusive) based on the dosing regimen defined below.

- For patients continuing QW: the population that patients continuing QW is defined as those continue QW throughout the study.
- For patients switching to Q2W: the population that patients switching to Q2W is defined as that switch from QW to Q2W at any timepoint.
- For patients switching back to QW from Q2W: the population that patients switching back to QW from Q2W is defined as those switches from Q2W to QW at any timepoint.

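### SAP 13.1.5: the switched-to-Q2W subgroup carries scores earned on weekly dosing and measures change from extension baseline, so it does not isolate whether Q2W maintains efficacy

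*SAP*

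**What the plan says.** Protocol 4.3 gives the purpose of the lower frequency: "For responders a Q2W regimen has been selected to evaluate whether a less frequent dosing regimen can maintain clinical efficacy".

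SAP 13.1.5 summarises "actual scores and changes from baseline in ESSDAI, clinESSDAI, and ESSPRI at scheduled timepoint of week 16, 24, 36 and 48". It then adds that "the same analysis in clinESSDAI and ESSDAI will be assessed for three subgroups (mutually exclusive) based on the dosing regimen defined below". The first subgroup is those on QW throughout. The second reads: "the population that patients switching to Q2W is defined as that switch from QW to Q2W at any timepoint". In the third, "patients switching back to QW from Q2W is defined as those switches from Q2W to QW at any timepoint".

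For the change scores, SAP 6.2 states that "baseline is defined as the last available non-missing measurement from the parent study 2106", and the plots in 13.1.5 use OLE baseline. Nothing in 13.1.5 sets a baseline at the switch or limits the Q2W subgroup to scores obtained after it.

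On timing, the Schedule of Activities puts all assessments before the infusion. It makes baseline, week 16 and week 24 switch points, and protocol 4.1 adds weeks 32, 36, 40 and 44 for participants still on QW. Footnote k limits the week 32 to 44 clinESSDAI to week-24 nonresponders who are not judged therapeutic failures.

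On responder status, the synopsis says: "Responder status will be determined by clinESSDAI assessments conducted on day 1, week 16, and week 24 and using the baseline of the qualifying study". Protocol 4.1 instead defines the reference as the final visit of the qualifying study.

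**The concern.** This is the only score analysis by regimen in the readable part of the SAP, so it is where a reader will look for evidence on Q2W. The subgroup is defined by the regimen a participant eventually reaches, while the visits shown include the time before that regimen began. A participant who first responds at week 40 sits in the Q2W subgroup with week 16, 24 and 36 scores all produced by weekly dosing.

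Membership also depends on the outcome being summarised. clinESSDAI decides who switches to Q2W, and a worsening clinESSDAI decides who goes back to QW. If those who go back are taken out of the Q2W subgroup, what remains is selected for not having worsened. At stake is whether the table can be read as showing that Q2W holds a response or loses it.

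**Working it through.** The plan states no figure to reproduce: no hypothesis is tested and the sample of about 30 is not calculated. The check is a cross-tabulation followed by simple arithmetic.

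**1. Which scores are earned on QW.** Switch times: day 1 and weeks 16, 24 (Schedule of Activities), 32, 36, 40, 44 (protocol 4.1). Reported visits: weeks 16, 24, 36, 48 (SAP 13.1.5). Assessment precedes dosing, so a score at or before the switch visit belongs to QW. Cells show weeks on Q2W at the visit.

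| Switch | Wk 16 | Wk 24 | Wk 36 | Wk 48 |
|---|---|---|---|---|
| Day 1 | 16 | 24 | 36 | 48 |
| Wk 16 | QW | 8 | 20 | 32 |
| Wk 24 | QW | QW | 12 | 24 |
| Wk 32 | QW | QW | 4 | 16 |
| Wk 36 | QW | QW | QW | 12 |
| Wk 40 | QW | QW | QW | 8 |
| Wk 44 | QW | QW | QW | 4 |
| Earned on QW | 6 of 7 | 5 of 7 | 3 of 7 | 0 of 7 |

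That is 14 of 28 cells. These are possible patterns, not patients.

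The week-36 column applies in full only to ESSDAI, which is scheduled for everyone. Under footnote k, and because the later assessments stop once response is confirmed, the week-36 clinESSDAI row of this subgroup would come mainly from participants switching at weeks 36 to 44, who are all still on QW.

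**2. What remains at week 48.** Let f be the share of later switchers, g the change on QW before the switch and w the change on Q2W. If day-1 starters are pooled with later switchers:

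mean change from OLE baseline = (1 − f)·w + f·(g + w) = w + f·g

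The change since the switch is w, so the gap is f·g. The inputs are assumptions; the documents give none.

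- f = 0.4, g = −5, w = +1: 1 + 0.4 × (−5) = −1.0. Everyone worsens by 1 point on Q2W, yet the table shows an improvement of 1 point.
- Range of the gap: 0.2 × 3 = 0.6 to 0.6 × 5 = 3.0 points in favour of Q2W.
- If day-1 starters are not in the group, f = 1 and the gap is the whole QW gain.

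**3. Do the three groups partition the participants?**

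| Path | SAP 13.1.5 group | SAP Table D class |
|---|---|---|
| QW throughout | first | QW |
| Q2W from day 1, stays | second, or none | Q2W |
| QW, then Q2W | second | SQ2W |
| Q2W from day 1, then QW | third (also second if day 1 counts as a switch) | SQW |
| QW, Q2W, QW | second and third | none |

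Whether day-1 starters belong to the second group is unclear. The Schedule of Activities and Table D call day 1 a switch, but the wording in 13.1.5 requires a move from QW.

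**4. Effect of moving reverters.** A simulation with no drug or regimen effect assumed constant true clinESSDAI (mean 9, SD 3), visit noise SD 1.5 to 3.5, scores rounded and floored at 0, and the qualifying-study baseline for response. With everyone who ever switches pooled, the week-24 mean change from OLE baseline is 0.00. If day-1 starters who meet the reversion rule at week 16 or 24 (59 to 73% of them) go to the third group, the remaining Q2W group shows −0.6 to −2.1. This assumes every such worsening is detected; in the protocol, reversion follows an unscheduled visit.

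**5. Former-placebo share.** "Participants were randomized to receive efgartigimod IV 10 mg/kg or matching placebo in a 2:1 ratio", so if 30 roll over in that ratio, about 10 come from placebo. The share of day-1 responders from placebo is 10·p / (20·e + 10·p), where e and p are assumed response rates on efgartigimod and placebo. For e = p = 50% it is 5/15 = 33%; for e = 70%, p = 30% it is 3/17 = 18%.

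**The case against.** The strongest case on the other side has five parts.

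- **The study is descriptive.** No hypothesis is tested, results are not to be used inferentially, and maintenance on Q2W is a dose rationale, not a listed objective. This stands and limits the severity. A descriptive table should still describe the regimen it names.
- **Other analyses bear on durability.** Protocol 9.3.4 plans a Kaplan-Meier analysis of reverting to QW and counts by regimen and by clinESSDAI score, and 13.1.5 also shows actual scores. SAP 13.2 and 13.3 are redacted and may hold more. A reader might therefore infer too much from this point, namely that the plan can show nothing about Q2W. The documents do not support that. But the Kaplan-Meier time runs from first infusion, not from the switch, and reports no scores.
- **Day-1 starters are measured correctly.** For those from the efgartigimod arm, OLE baseline is the switch point, so their change does measure maintenance. This stands. The difficulty is that 13.1.5 does not show them on their own.
- **Former-placebo participants are separable.** A reader might infer that placebo responders contaminate every Q2W result. SAP 7.2 gives summaries overall and by parent arm, so mixing across arms is certain only in the overall column. However, 13.1.5 does not say that its subgroups are crossed with parent arm. If they are, the former-placebo column could still combine day-1 Q2W starters with participants who first had at least 16 weeks of weekly efgartigimod. Day-1 response on placebo also presupposes the synopsis baseline. Under protocol 4.1 the day-1 change is zero by construction.
- **Pooling need not bias the mean.** A reader might infer that selection on clinESSDAI alone makes the pooled Q2W mean look favourable. The no-effect simulation does not show this: pooled, the change is 0.00. The bias appears when reverters are moved out.

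**Conclusion.** The point holds as a limit on what the 13.1.5 subgroup table can show. As defined, the Q2W subgroup reports QW-earned scores at weeks 16, 24 and 36, carries the pre-switch gain into week 48, and leaves two regimen paths without a unique place. Its change from OLE baseline therefore does not isolate maintenance on Q2W.

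The pattern counts follow from the documents alone. The 0.6 to 3.0 point gap rests on assumed shares and gains. The −0.6 to −2.1 selection effect rests on the simulation's assumptions and on reverters being assigned to the third group, which the SAP does not settle. Neither figure predicts this trial's result. The primary safety objective is unaffected. This should be corrected before the final analysis, but it does not invalidate the plan.

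**What to change.** In SAP 13.1.5:

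1. Replace the three subgroups with the Table D classes (QW, Q2W, SQ2W, SQW), crossed with parent arm. Add a class or rule for the QW, Q2W, QW path, which Table D does not cover: SQW starts on Q2W and SQ2W ends on Q2W.
2. For participants who receive Q2W, add the change from the last score before the first Q2W dose, using post-switch scores only, by weeks since the switch.
3. Keep reverters in the denominator of those who started Q2W.
4. Show former-placebo day-1 Q2W starters separately.
5. State that some rise after the switch is expected, because participants switch on a low score.

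The protocol passages on the responder baseline (synopsis and schema against section 4.1) must be reconciled, since they determine who can be a day-1 responder.

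The cost is SAP wording and one reworked table from data already collected. The drawback is small rows: with about 30 participants some cells will hold only a few people, so individual profiles may be more informative than means.

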14. PHARMACODYNAMIC ANALYSIS

PD analyses will be performed in the SAF. PD endpoints include total IgG, Anti-Ro/SS-A, and anti-La/SS-B. PD endpoints will be summarized using descriptive statistics at each analysis visit. Actual values, changes from baseline, and percent change from baseline will be presented. In addition to the planned time points at baseline, week 4, 8, 12, 16, 24, 36, 48, and SFV, the following time points will also be shown:

- Maximum drop from baseline
- Minimum postbaseline value

Additionally, a line chart showing percent change in total IgG, Anti-Ro/SS-A, and anti-La/SS-B, over time will be prepared. If appropriate, the graphic presentation of percent change over time may be presented for all PD endpoints combined. All PD data will be listed.

15. IMMUNOGENICITY ANALYSIS

Incidence and prevalence of ADAs against efgartigimod will be assessed in the SAF. ADAs to efgartigimod is measured at the time points specified in the schedule of activities of protocol, primarily at baseline, week 2, 4, 8, 12, 16, 24, 36, 48 and SFV.

Immunogenicity samples are analyzed in a 3-tiered approach:

- All samples are evaluated in the ADA screening assay and are scored ADA screening positive (tier 1) or negative.
- If a sample is scored positive in the ADA screening assay, it is further evaluated in the confirmatory assay (tier 2) and is scored confirmed positive (positive immuno-depletion) or confirmed negative (negative immuno-depletion).
- If a sample is scored as confirmed positive, the samples are further characterized in the ADA titration assay (to determine titer).

[figure not shown]
If available, a titer result will be reported for the ADA confirmed positive samples. However, a titer result is not

[figure not shown]
always available:

- If the ADA confirmed positive sample could not be run in the titration assay (e.g., due to insufficient sample volume/quality to perform the titer analysis), the result will be described as “positive immuno-depletion”, and the sample should be considered ADA positive.
 - If a sample is negative in the titration assay, it will be reported as “negative titer”, but it should be considered ADA positive because it was confirmed positive in the second tier.
 - If a sample could not be analyzed or reported as “positive screen”, the ADA sample status is ADA unevaluable.
- An overview of this 3-tiered approach and all possible ADA sample results that will be reported by the laboratory is given below. From these reported ADA sample results, a final ADA sample status must be derived during the statistical analysis, as presented in the final column (“Final ADA Outcome”):

Figure 2: ADA Sample Status

Copyright © 2009, 2010, 2012, 2016, 2018, 2019, 2021, 2024 IQVIA. All rights reserved. The contents of this document are confidential and proprietary to IQVIA Holdings Inc. and its subsidiaries. Unauthorized use, disclosure or reproduction is strictly prohibited.

^a “Positive titer” is reported if it was not possible to retrieve a numerical value.

Participant Classification for ADA Against Efgartigimod

Table G below gives an overview of how the ADA participant classification will be derived, starting from the participant baseline ADA sample status.

Table H: Participant Classification for ADA Against Efgartigimod

Participant ADA classification	Highest ^a postbaseline sample status				
	ADA negative	ADA positive (missing titer ^b)	ADA positive (negative titer ^c or numerical titer value)		ADA unevaluable
Baseline ADA sample status					
ADA negative	ADA negative	Treatment-induced ADA	Treatment-induced ADA		ADA unevaluable
ADA positive (missing titer^b)	Treatment-unaaffected ADA	ADA unevaluable	ADA unevaluable		ADA unevaluable
ADA positive (negative titer^c or numerical titer value)	Treatment-unaaffected ADA	ADA unevaluable	Titer <4x baseline titer: Treatment-unaaffected ADA	Titer ≥4x baseline titer: Treatment-boosted ADA	ADA unevaluable
ADA unevaluable	ADA unevaluable	ADA unevaluable	ADA unevaluable		ADA unevaluable

^a Highest sample status, with order (from low to high): ADA unevaluable, ADA negative, ADA positive (“positive immuno-depletion” or “positive titer”), ADA positive with titer <1 (“negative titer”), ADA positive with titer ≥1 (numerical value selecting the sample with highest titer).

^b Samples with missing titer will have a reported ADA result of “positive immuno-depletion” or “positive titer”.

^c Results reported as “negative titer”, i.e. titer value <1 will be set to a value of 1.

The following definitions will be used in the summary tables:

- ADA evaluable participant = participant classified in any of following categories: ADA negative, treatment-

unaffected ADA, treatment-induced ADA, or treatment-boosted ADA. The first 2 categories are classified as “ADA negative”, and the latter 2 are classified as “ADA positive”.

- ADA incidence = percentage of participants with treatment-induced or treatment-boosted ADA (denominator: number of evaluable participants).
- ADA prevalence = percentage of participants with treatment-unaffected ADA, treatment-induced ADA, or treatment-boosted ADA (denominator: number of evaluable participants).
- ADA unevaluable participant = participant classified as ADA unevaluable or with missing baseline ADA sample or without postbaseline ADA samples (in case no ADA data are available at all, the participant cannot be classified)

Note: A 4-fold difference in titer values is considered significant if a 2-fold serial dilution is applied (= 2 times the dilution factor).

Frequency tabulations (number and percentages) will be provided with ADA negative/positive/unevaluable samples per visit.

Frequency tabulations (number and percentages) will be provided in 1 table for:

- ADA unevaluable Participants
- ADA baseline positive/negative/unevaluable samples
- Participants per ADA participant classification
- Prevalence and incidence of ADA

Correlation tables by ADA against efgartigimod participant classification will be provided for the following parameters:

- Mean drug concentration over time
- Mean percent change from baseline in [total IgG]
- ClinESSDAI score at over time.
- TEAEs by MedDRA SOC and PT
- Serious TEAEs by MedDRA SOC and PT
- Injection/infusion-related reactions

ADA against efgartigimod titer values will be summarized using descriptive statistics by ADA participant classification at each analysis visit.

All available data for ADA against efgartigimod will be listed, while also showing the ADA sample status and participant classification.

Copyright © 2009, 2010, 2012, 2016, 2018, 2019, 2021, 2024 IQVIA. All rights reserved. The contents of this document are confidential and proprietary to IQVIA Holdings Inc. and its subsidiaries. Unauthorized use, disclosure or reproduction is strictly prohibited.

16. 

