9.3. Statistical Analyses

9.3.1. General Considerations

- Data collected will be listed with derived variables. Descriptive statistical methods will be used to analyze safety and efficacy data
- The results of this study will not be used inferentially
- No formal sample size calculation is presented
- Summaries will include the number of observations (n), mean, SE, 90% CI, median, minimum, and maximum for continuous measures
- Summaries will include sample size, frequencies, and percentages for categorical variables
- The baseline value will be the last assessment before the first administration of the study drug in OLE
- All study visits will be recalculated based on actual dates. The rules for calculating the analysis visits will be documented in the SAP
- Rules for imputing partial dates or missing dates will be provided in the SAP
- Exposure to IMP will be summarized
- TEAEs, AESIs, SAEs, and other safety parameters will be summarized
- AEs will be classified using the latest version of the MedDRA classification system
- AEs, AESIs, and SAEs will be listed corresponding to MedDRA SOC and PT

- Multiple occurrences of a single PT in a participant will be counted only once at the maximum severity/grade
- AEs with missing severity or relationship to IMP will be classified as severe and treatment-related, respectively. All AEs will be summarized by relatedness to IMP
- Any AEs leading to death or discontinuation of IMP will also be summarized
- Population PK/PD analysis may be performed based on the PK and PD data and reported separately
- Laboratory parameters, physical examinations, vital sign measurements, ECG data and PK, PD, immunogenicity, and biomarker results will be summarized descriptively

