6.3. Windowing Conventions

All assessments, including unscheduled assessments, will be allocated to an analysis visit window. Tables and listings will be based on analysis windows defined below. Allocations of assessments will be performed using their relative day.

Table B: Non-efficacy Analysis Visit Definition (immunogenicity)

Phase	Target Day	Assigned Study Day		Week Assigned
		Assigned (Inclusive) From	To	
Treatment	Not applicable ^a			Baseline
	15	1 ^a	22	Week 2
	29	23	43	Week 4
	57	44	71	Week 8
	85	72	99	Week 12
	113	100	141	Week 16
	169	142	211	Week 24
	253	212	295	Week 36
	337	296	Up to the date of SFV.	Week 48
Safety Follow-up	NA	NA	NA	SFV

confidential and proprietary to IQVIA Holdings Inc. and its subsidiaries. Unauthorized use, disclosure or reproduction is strictly prohibited.

^a Last available non-missing measurement from the parent study ARGX-113-2106.

For QW regimen, the final dose will be administrated at week 47. For Q2W regimen, the final dose will be administered at week 46.

After treatment period ends, safety follow-up will be approximately 7 weeks (56 days ± 3 days) will be summarized separately.

[figure not shown]
The above [Table B](#) contains visit window for every assessment's visited (e.g., Immunogenicity). Refer to respective visit window table for other assessments.

Some parameters which are not collected at every visit, visit window will be combined (by extending window with previous or subsequent visits).

[figure not shown]
For e.g. Week 2 are not protocol scheduled visit for brief physical examination (symptom driven), vital signs, electrocardiogram (ECG), clinical laboratory assessments, total IgG, anti-Ro/SS-A, anti-La/SS-B autoantibodies. Hence, visit window can be combined with baseline and week 4. The non-missing value closest to the target day will be used in the analysis in case of multiple observations.

Table B: Non-efficacy Analysis Visit Definition for brief physical examination (symptom driven), vital signs, electrocardiogram (ECG), clinical laboratory assessments, total IgG, anti-Ro/SS-A, anti-La/SS-B autoantibodies.

Phase	Target Day	Assigned Study Day (Inclusive)		Week Assigned
		From	To	
Treatment	Not applicable ^a			Baseline
	29	2	43	Week 4
	57	44	71	Week 8
	85	72	99	Week 12
	113	100	141	Week 16
	169	142	211	Week 24
	253	212	295	Week 36
	337	296	Up to the date of SFV.	Week 48
Safety Follow-up	NA	NA	NA	SFV

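### For participants who came from the parent efgartigimod arm, ADA already present at OLE baseline is labelled treatment-unaffected and grouped as ADA negative, although the drug may have induced it

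*SAP*

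**What the plan says.** **Baseline.** SAP Section 6.2 states that, unless otherwise specified, "baseline is defined as the last available non-missing measurement from the parent study 2106", and adds: "These baseline observations could be either from week 24 or prior visits of ARGX-113-2106". The immunogenicity visit-window table in SAP Section 6.3 repeats the rule in its footnote: "Last available non-missing measurement from the parent study ARGX-113-2106". Section 15 specifies no exception for ADA. Protocol Section 9.3.1 uses the same anchor: "The baseline value will be the last assessment before the first administration of the study drug in OLE".

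**Exposure before that baseline.** Protocol Section 2 says of the parent study: "Participants were randomized to receive efgartigimod IV 10 mg/kg or matching placebo in a 2:1 ratio". Dosing was weekly, and "The final dose was administered at week 23". Both parent arms roll over.

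**Classification.** Under Table H in SAP Section 15, a participant who is ADA positive with a usable titre at baseline is treatment-unaffected if the OLE samples are negative or the highest OLE titre is below 4 times baseline. At 4 times or more the participant is treatment-boosted. The definitions under the table put ADA negative and treatment-unaffected together ("The first 2 categories are classified as" ADA negative) and put induced and boosted together as ADA positive. Incidence is induced plus boosted over evaluable participants. Prevalence adds the treatment-unaffected.

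**Use.** "Correlation tables by ADA against efgartigimod participant classification will be provided" for drug concentration, total IgG, clinESSDAI, TEAEs, serious TEAEs and infusion-related reactions.

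**The concern.** The term treatment-unaffected presumes a baseline taken before any exposure to the drug. That is true of former-placebo participants, whose ADA at OLE baseline is properly pre-existing. It is not true of former-efgartigimod participants, for whom ADA at OLE baseline may itself be the product of about 24 weeks of treatment. Calling it unaffected by treatment, and then placing it with the negatives, contradicts what the data would show.

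Two things are at stake:

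- A reader of the incidence figure, a secondary endpoint, may take it as the rate at which efgartigimod induces ADA, when the participants with the longest exposure can contribute to it only through a 4-fold boost.
- Any table built on the two-way split compares ADA positive participants with a group that includes ADA carriers. If four categories are shown instead, the treatment-unaffected one still mixes possibly drug-induced with truly pre-existing ADA.

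**Working it through.** The documents give no ADA rate, so there is no planned figure to reproduce. The check applies Table H to example profiles and then works out the effect on the summary measures.

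**Step 1. Table H on participants who were ADA negative before the parent study (illustrative titres).**

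| OLE baseline | Highest OLE result | Class under the SAP | Class against a sample before the first parent dose |
|---|---|---|---|
| titre 8 | negative | treatment-unaffected, grouped as ADA negative | treatment-induced |
| titre 8 | 8 or 16 | treatment-unaffected, grouped as ADA negative | treatment-induced |
| titre 8 | 32 (4 × 8) | treatment-boosted, counted as incident | treatment-induced |
| positive, titre missing | positive | unevaluable, out of the denominator | treatment-induced |

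The misclassification therefore affects carriers who are not boosted. It does not affect every carrier.

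**Step 2. Effect on incidence and on the ADA negative group.**

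Inputs: up to about 30 participants (SAP Section 3.2) and 2:1 allocation (Protocol Section 2). Assumptions: all 30 are evaluable, and rollovers keep the 2:1 ratio, giving 30 × 2/3 = 20 former-efgartigimod and 10 former-placebo participants.

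Let *k* be former-efgartigimod participants with parent-induced ADA at OLE baseline, *b* those of them boosted at least 4-fold, and *i* the new cases induced in the OLE.

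- SAP incidence = (i + b)/30
- Incidence since first exposure = (i + k)/30
- Gap = (k − b)/30, so 1/30 = 3.3 points per carrier not boosted
- Share of the ADA negative group with parent-induced ADA = (k − b)/(30 − i − b)

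With i = 2 and b = 0, both assumed:

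| k (assumed) | SAP incidence | Incidence since first exposure | Share of ADA negative group |
|---|---|---|---|
| 1 | 2/30 = 6.7% | 3/30 = 10.0% | 1/28 = 3.6% |
| 2 | 2/30 = 6.7% | 4/30 = 13.3% | 2/28 = 7.1% |
| 4 | 2/30 = 6.7% | 6/30 = 20.0% | 4/28 = 14.3% |
| 8 | 2/30 = 6.7% | 10/30 = 33.3% | 8/28 = 28.6% |

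For k = 4, the exact 90% intervals are 1.2 to 19.5% for SAP incidence and 9.1 to 35.7% for incidence since first exposure. If every carrier is boosted (b = k), the gap and the share are both 0. SAP prevalence is (i + k)/30, so it includes these participants, but it does not say which of them were drug-induced.

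**Step 3. Incidence read strictly as OLE-only.** The denominator still holds carriers who cannot become treatment-induced. With k = 4, i = 2 and b = 0, the SAP gives 2/30 = 6.7%, against 2/(30 − 4) = 2/26 = 7.7% among those ADA negative at OLE baseline.

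**The case against.** The strongest case for the plan is that it does what its endpoint says. The endpoint is ADA incidence and prevalence across the 48 weeks of OLE treatment, and Protocol and SAP agree on an OLE baseline. ADA first seen in the parent study is not new in the OLE, so leaving it out of OLE incidence is not an error. This stands.

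Much of the information is also already planned. Prevalence counts these participants. SAP Section 15 tabulates baseline ADA status and every classification category, and lists all results. SAP Section 7.2 provides summaries by parent treatment. A careful reader could find the affected participants. This stands too, but none of it changes the label or the two-way grouping.

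Two stronger readings are tempting, and the documents do not support either:

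- *The incidence endpoint is understated.* That holds only for incidence since first exposure, which neither document sets out to estimate.
- *The ADA correlation tables are contaminated and biased toward no effect.* Those tables are planned by participant classification. If all Table H categories are shown, the ADA negative column contains nobody who was positive at OLE baseline. Mixing occurs only if the two-way grouping is used there, which the SAP does not settle. Some treatment-unaffected participants will also be negative at every evaluable OLE sample and so are not carriers during the OLE. The study is descriptive, with no hypothesis test.

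**Conclusion.** The point holds as a classification fault limited to former-efgartigimod participants who are ADA positive at OLE baseline. For them, treatment-unaffected is the wrong description and ADA negative the wrong group. Any summary that uses the two-way grouping would mix carriers with negatives. The OLE-period incidence is defensible as worded, but its scope should be stated, and its denominator includes participants who cannot become treatment-induced.

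The size cannot be fixed from the documents. Under the assumptions of 30 evaluable participants and a 20:10 split, each carrier who is not boosted accounts for at most 3.3 points of pooled incidence since first exposure. If 5%, 10% or 20% of the 20 carried parent-induced ADA (k = 1, 2 or 4), the gap is at most 3.3, 6.7 or 13.3 points. These are upper values: they require that the ADA persists to the last parent sample, that none is boosted, and that none becomes unevaluable through a missing titre. The gap can be 0.

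**What to change.** Amend SAP Section 15:

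1. Report participants from the parent efgartigimod arm who are ADA positive at OLE baseline as their own category, for example *ADA positive at OLE baseline after prior efgartigimod*, in all summary and correlation tables. Do not show them as treatment-unaffected or within ADA negative. Former-placebo participants need no change.
2. State that incidence refers to the OLE only, and give treatment-induced incidence among participants ADA negative at OLE baseline, by parent arm. The parent-arm split is already planned.
3. If ADA samples from before the first parent dose exist, which these documents do not confirm, add a supplementary incidence since first exposure for the former-efgartigimod arm and say which parent-study samples count as postbaseline. Report it separately from the former-placebo arm, because the periods at risk differ: about 24 + 48 = 72 weeks against 48. It should not replace the planned endpoint.

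Items 1 and 2 cost SAP wording and one extra category with small counts. Item 3 also needs a merge with parent-study data.
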